9.2 Safety

The objective is to describe the clinical safety profile of VRVg-2 (low, medium and high dosage) versus VRVg-1 and Imovax Rabies, after each vaccine injection.

9.2.1 Safety Definitions

The following definitions are taken from the ICH E2A Guideline for Clinical Safety Data Management: Definitions and Standards for Expedited Reporting.

Adverse Event (AE):

An AE is any untoward medical occurrence in a patient or clinical investigation subject administered a pharmaceutical product and which does not necessarily have to have a causal relationship with this treatment. An AE can therefore be any unfavorable and unintended sign (including an abnormal laboratory finding, for example), symptom or disease temporally associated with the use of a medicinal product, whether or not considered related to the medicinal product.

Therefore an AE may be:

- A new illness
- The worsening of a concomitant illness
- An effect of the vaccination, including the comparator
- A combination of the above

All AEs include serious and non-serious AEs.

Surgical procedures are not AEs; they are the action taken to treat a medical condition. It is the condition leading to the action taken that is the AE (if it occurs during the trial period). Planned and scheduled surgery is not considered as an SAE and should be recorded at the time of inclusion in the trial.

Pre-existing medical conditions are not to be reported as AEs. However, if a pre-existing condition worsens in frequency or intensity, or if in the assessment of the treating physician there is a change in its clinical significance, this change should be reported as an AE (exacerbation). This applies equally to recurring episodes of pre-existing conditions (e.g., asthma) if the frequency or intensity increases post-vaccination.

Serious Adverse Event (SAE):

Serious and *severe* are not synonymous. The term *severe* is often used to describe the intensity of a specific event as corresponding to Grade 3. This is not the same as *serious* which is based on patient / event outcome or action criteria usually associated with events that pose a threat to a patient's life or functioning. Seriousness, not severity, serves as a guide for defining regulatory reporting obligations.

An SAE is any untoward medical occurrence that at any dose (including overdose):

- Results in death
- Is life-threatening^a
- Requires inpatient hospitalization or prolongation of existing hospitalization^b
- Results in persistent or significant disability / incapacity^c
- Is a congenital anomaly / birth defect
- Is an important medical event^d

Adverse Reaction:

All noxious and unintended responses to a medicinal product related to any dose should be considered adverse reactions (AR).

(The phrase “responses to a medicinal product” means that a causal relationship between a medicinal product and an AE is at least a reasonable possibility)

Unexpected Adverse Reaction (UAR):

An unexpected adverse reaction is an AR, the nature or severity of which is not consistent with the applicable product information (e.g., Investigator's Brochure for an unapproved investigational medicinal product).

^a The term “life-threatening” refers to an event in which the subject was at risk of death at the time of the event; it does not refer to an event which hypothetically might have caused death if it were more severe.

^b All medical events leading to hospitalizations will be recorded and reported as Serious Adverse Events, with the exception of: hospitalization planned before inclusion into the study or out-patient treatment with no hospitalization.

^c “Persistent or significant disability or incapacity” means that there is a substantial disruption of a person’s ability to carry out normal life functions.

^d Medical and scientific judgment should be exercised in deciding whether expedited reporting is appropriate in other situations, such as important medical events that may not be immediately life-threatening or result in death or hospitalization but may jeopardize the health of the subject or may require intervention to prevent one of the other outcomes listed in the definition above. These should also usually be considered serious. Examples of such events include allergic bronchospasm requiring intensive treatment in an emergency room or at home, blood dyscrasias or convulsions that do not result in inpatient hospitalization, or the development of drug dependency or drug abuse, new onset diabetes, or autoimmune disease.

The following additional definitions are used by Sanofi Pasteur:

Solicited Reaction:

A solicited reaction is an event that is prelisted in the CRF. The assessment of these AEs post-vaccination is mandatory. A solicited reaction is defined by a combination of:

- Symptom and
- Onset post-vaccination

e.g., injection site pain between D0 and D03 post-vaccination, or headache between D0 and D07 after the last vaccination.

A solicited reaction is therefore an AR observed and reported under the conditions (symptom and onset) prelisted (i.e., solicited) in the CRF and considered as related to vaccination.

Unsolicited AE / AR:

An unsolicited AE is an observed AE that does not fulfill the conditions prelisted in the CRF in terms of diagnosis and / or onset post-vaccination, i.e., excluding solicited reactions, e.g., if headache between D0 and D7 is a solicited reaction (i.e., prelisted in the CRF), then a headache starting on D7 is a solicited reaction, whereas headache starting on D8 post-vaccination is an unsolicited AE.

An unsolicited non-serious AE is an unsolicited AE excluding SAEs.

Injection Site Reaction:

An injection site reaction^a is an AR at and around the injection site. Injection site reactions are commonly inflammatory reactions.

Systemic AE:

Systemic AEs are all AEs that are not injection site reactions. They therefore include systemic manifestations such as headache, fever, as well as localized or topical manifestations that are not associated with the vaccination site, e.g., erythema that is localized but that is not at the injection site.

In addition, reactions reported at the site(s) of HRIGs administration will be reported as systemic AEs.

^a All injection site AEs are considered to be related to vaccination and are therefore all *injection site reactions*.

Adverse Events of Special Interest (AESIs):

AEs of special interest are AEs that are considered by the Sponsor to be relevant for the monitoring of the safety profile of the investigational vaccine. The following AESIs are defined: anaphylactic reactions, encephalitis and convulsions.

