6.3 Identity of Other Product

Licensed HRIGs (Imogam® Rabies) will be administered at D0 in all subjects included in the trial for simulated post-exposure treatment.

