6.3.2 Preparation and Administration

Imogam® Rabies is a ready-to-use, colorless to light opalescent solution for injection. The volume to be injected per subject is to be calculated based on the body weight as presented in the table below.

Weight (kg)	Quantity of HRIG (IU)	Volume (mL)	Number of injections
60	1200	8	2
80	1600	10.67	3
100	2000	13.33	3
120	2400	16	4

A 5-mL syringe will be used and will be filled using several vials as necessary. The content of the syringe should be injected by the IM route at a body site distant from the rabies vaccine injection site (anterolateral thigh). A maximum of 5 mL is to be administered by injection; the total volume will be divided and administered at separate sites (sites should be at least 3 cm apart).

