9.2.2 Safety Endpoints

The primary endpoint(s) for the evaluation of safety are:

- Occurrence of any unsolicited systemic adverse events (AEs) reported in the 30 minutes after each vaccine injection

Collection of injection site reactions:

- Occurrence of solicited (prelisted in the subject's diary card [DC] and electronic case report form [CRF]) injection site reactions occurring within 7 days after each injection
- Occurrence of unsolicited (spontaneously reported) injection site reactions occurring within 28 days after each injection

Collection of systemic reactions and AEs:

- Occurrence of solicited (prelisted in the subject's DC and CRF) systemic reactions between the first and the second injections as well as between the second and the third injections, and up to 7 days after the remaining injections.
- Occurrence of unsolicited (spontaneously reported) systemic AEs between each injection and up to 28 days after the last injection.
- Occurrence of serious adverse events (SAEs) throughout the trial.

Other endpoints recorded or derived will be described at the time of statistical analysis plan. Depending on the item, these could include: nature (Medical Dictionary for Regulatory Activities [MedDRA] preferred term), time of onset, duration, number of days of occurrence, grade of severity, relationship to vaccine, action taken, whether the AE led to early termination from the study, seriousness, or outcome.

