|-----------------|--|----------------|
| Post-dose 3,4,5 | | D0-D3 D4-D7 |
|-----------------|--|----------------|

- Range of number of days of occurrence categories are in Table 5.3

Table 5.3: Range of Number of Days of Occurrence Categories for Solicited Reactions during the solicited period

| | Injection Site Reactions | Systemic Reactions |
|------------------|------------------------------------|--------------------------|
| Post-dose 1 | 1 - 3 days 4 - 7 days 8 days | 1 - 3 days 4 days |
| Post-dose 2 | | 1 - 3 days 4 - 5 days |
| Post-dose 3, 4,5 | | 1 - 3 days 4 - 7 days |

Solicited reaction after any injection

“After any injection” means after the five scheduled vaccine injections, and at least after the first vaccine injection (D0).

The solicited reaction will be presented after any injections according to:

- Overall occurrence over the D0-D7 period for injection site reactions or between vaccinations for systemic reactions (up to D7 for the last 2 vaccinations)
- Time of onset period
- Intensity grade: the maximum intensity grade will be computed during the solicited period for all solicited reactions and overall for on-going solicited reactions.

30-minutes Post-Vaccination Observation Period

Unsolicited systemic AEs occurring within 30 minutes after each vaccination will be presented in summary safety tables, analyzed according to their nature (SOC and PT of the MedDRA classification) and will be listed.

Unsolicited Adverse Events

The unsolicited non-serious AEs will be analyzed

- “Between the first and the second vaccine injection”, which corresponds to AEs reported at V02 and occurring after the first vaccine injection †

† For subjects interrupting their vaccination schedule after the first injection, unsolicited AEs until 28 days after the first injection are collected at visit V02

- “Between the second and the third vaccine injection”, which corresponds to AEs reported at V03 and occurring after the second vaccine injection [†]
- “Between the third and the fourth vaccine injection”, which corresponds to AEs reported at V04 and occurring after the third vaccine injection [§]
- “Between the fourth and the fifth vaccine injection”, which corresponds to AEs reported at V05 and occurring after the fourth vaccine injection ^{**}
- “Within 28 days after the fifth vaccine injection”, which corresponds to AEs reported at V07 and occurring after the fifth vaccine injection

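### Local reactions at the HRIG thigh sites count as systemic AEs and the SAP never separates them, so unsolicited systemic AE rates after dose 1 carry another product's local reactions

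*Protocol*

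**What the plan says.** Protocol Section 9.2.1 defines systemic AEs as everything that is not an injection site reaction, including "localized or topical manifestations that are not associated with the vaccination site". It then applies this to HRIG explicitly: "reactions reported at the site(s) of HRIGs administration will be reported as systemic AEs".

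HRIG "will be administered at D0 in all subjects included in the trial" (Protocol Section 6.3). Section 6.3.2 places it intramuscularly in the anterolateral thigh, away from the vaccine site, and adds that "A maximum of 5 mL is to be administered by injection" and that "the total volume will be divided and administered at separate sites". Its weight table runs from 2 injections at 60 kg to 4 at 120 kg.

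Protocol Section 9.2.2 lists first among its safety endpoints: "Occurrence of any unsolicited systemic adverse events (AEs) reported in the 30 minutes after each vaccine injection". Section 9.2.3.1 treats vaccine-site reactions in the same half hour differently: they are recorded as starting on the day of vaccination, not as immediate events.

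SAP Section 4.2 refers back to Protocol Section 9.2 for safety definitions. SAP Section 5.1.2.2.1 says that "Unsolicited systemic AEs occurring within 30 minutes after each vaccination will be presented in summary safety tables". It breaks unsolicited AEs down by vaccine received, injection interval, SOC and PT, causality to the vaccine, onset, duration and intensity. Apart from the abbreviations and design text, the SAP mentions HRIG only in the per-protocol rule on the amount of Imogam given.

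**The concern.** The safety objective is to describe each vaccine's profile after each injection. A sore or red thigh from HRIG is neither systemic nor a vaccine effect, yet it counts as an unsolicited systemic AE in the vaccine tables.

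Two things make this more than a labelling matter.

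- HRIG is given only with dose 1. Its site reactions load mainly onto the first injection interval, and randomization does not balance a comparison of doses within a group.
- The 30-minute endpoint becomes asymmetric. A local reaction at the vaccine site stays out of it, while a local reaction at the HRIG site enters it, at D0 only.

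A reader of the report could take a higher unsolicited systemic rate after the first injection as a property of the vaccine.

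**Working it through.** **The plan's own figure.** The only visible safety precision figures are in Protocol Table 12.2 (SAP Table 5.5), for n = 80. The Clopper-Pearson limits are the 0.025 quantile of Beta(x, n − x + 1) and the 0.975 quantile of Beta(x + 1, n − x). For x = 8 this gives 10.0% (4.4; 18.8). All five rows reproduce to one decimal, so no stated figure is in dispute.

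**Where the events go.** Follow a thigh-site reaction that starts on D0:

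1. Protocol 9.2.1 makes it a systemic AE.
2. The solicited systemic reactions are four prelisted terms: fever, headache, malaise and myalgia (Protocol Table 9.2). Thigh redness or swelling is none of these, so it is unsolicited. Thigh pain might be recorded as myalgia, because the exclusion in that table covers only the injection site and does not say whether an HRIG site counts.
3. SAP 5.1.2.2.1 counts it between the first and second injections and in the any-injection total.
4. If it starts within 30 minutes, it also enters the immediate summary.
5. No later step identifies it as an HRIG-site event.

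**Exposure.** At 20 IU/kg and 150 IU/mL the volume is 20 × weight / 150: 8 mL at 60 kg and 16 mL at 120 kg. At most 5 mL per injection gives 2 and 4 injections, as in the table. Four are needed only above 15 × 150 / 20 = 112.5 kg. With BMI capped at 30, that means a height of at least √(112.5 / 30) ≈ 1.94 m, so two or three injections will be usual.

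**Size.** Let p be the proportion of subjects with an unsolicited systemic AE other than an HRIG-site event, and h the proportion with an HRIG-site reaction. The documents give no value for h, so it is assumed over a range. If the two are independent, the reported rate is 1 − (1 − p)(1 − h), an increase of h(1 − p).

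| Assumed h | True p = 10% reads | True p = 20% reads | 10-point group difference becomes |
|---|---|---|---|
| 2% | 11.8% | 21.6% | 9.8 points |
| 5% | 14.5% | 24.0% | 9.5 points |
| 10% | 19.0% | 28.0% | 9.0 points |
| 20% | 28.0% | 36.0% | 8.0 points |
| 30% | 37.0% | 44.0% | 7.0 points |

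For example, at p = 10% and h = 10%: 1 − 0.90 × 0.90 = 19.0%.

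**Across doses.** Suppose the true rate is 10% after dose 1 and after a later dose, and all HRIG-site reactions start before dose 2. The tables would show 14.5% v 10% at h = 5%, 19.0% v 10% at h = 10%, and 28.0% v 10% at h = 20%. The whole gap would come from HRIG-site events. For scale, 19.0% lies just above the 18.8% upper limit that Table 12.2 gives for 8/80.

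**Across groups.** With the same h in every arm, the difference is (p₂ − p₁)(1 − h), which is the last column of the table.

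**The case against.** The strongest reply is that this is a deliberate, disclosed convention. Systemic is a residual category, the protocol and SAP agree on it, and the rule usefully keeps thigh reactions out of the vaccine's injection-site profile. That stands. The weakness is not the definition but the absence of any SAP output that makes these events visible.

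Second, some separation already exists. Protocol 9.2.3.3 lets the investigator rate an event as not related when concomitant therapy is the likely cause, which would take it out of the vaccine-related counts, and PT tables may show site-type terms. This stands in part. Neither breakdown identifies the thigh or HRIG, and SAP Section 5.3.2.2 counts missing causality as related to vaccination.

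Third, a reader might infer that the mixing biases the choice of dosage or hides differences between groups. The documents do not support this. All five randomized groups receive HRIG, so no arm is favoured in expectation. The SAP plans per-group percentages with exact intervals, no safety test, and no between-group safety ratio. A 20% v 10% ratio of 2.00 would fall to 1.66, 1.47 or 1.29 at h = 5%, 10% or 20%, but that is not a planned statistic. The risk difference moves little.

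Fourth, h may be small. The HRIG risk section of the protocol names no local reaction, although it rests on voluntary reports and so gives no rate. Some events may also drop out: under SAP Sections 4.3.1.2.1 and 4.3.1.2.2, redness or swelling under 25 mm would be graded as none and excluded if coded to a PT on the solicited list. Both points stand as limits on the size.

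Last, the dose intervals already differ in length, so dose-by-dose unsolicited rates need care anyway. True, but the HRIG-site events fall mainly in the shortest interval and add a second, avoidable difference.

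**Conclusion.** The point holds as a reporting gap confined to unsolicited systemic AEs: the rates after dose 1 and after any dose, and the 30-minute rate at D0. Those rates are raised in every group by h(1 − p), and dose 1 is not like for like with doses 2 to 5. It is not a bias between arms, it largely spares the solicited systemic reactions, and no planned test or stated figure is wrong.

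The size cannot be obtained from the documents. The figures of 14.5%, 19.0% and 28.0% for a true 10% rest on assumed values of h (5%, 10%, 20%), on independence, and on every HRIG-site event being counted. If h is near 2%, the shift is under 2 points. This is a cheap improvement, not a threat to the trial's conclusions. It would also remove only the local part: systemic effects of HRIG at D0 cannot be told apart from those of dose 1 in this design.

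**What to change.** In SAP Section 5.1.2.2.1:

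- Define a flag for reactions at an HRIG administration site, assigned from the verbatim term at the blind data review already planned (Protocol Section 11.3, SAP Section 5.6). Query the site where the location is unclear. Because every arm receives HRIG, the flag reveals no allocation.
- Tabulate flagged events as their own category, by group.
- Present immediate, post-dose-1 and any-dose unsolicited systemic AEs with these events, as the protocol defines them, and without them.
- State whether the 25 mm grading rule applies to redness and swelling at HRIG sites.

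The cost is one derived flag, a few table rows and possibly some queries. The protocol definition is unchanged and no new data item is needed. The flag's accuracy depends on whether the verbatim terms name the site.

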9.2.2 Safety Endpoints

The primary endpoint(s) for the evaluation of safety are:

- Occurrence of any unsolicited systemic adverse events (AEs) reported in the 30 minutes after each vaccine injection

Collection of injection site reactions:

- Occurrence of solicited (prelisted in the subject's diary card [DC] and electronic case report form [CRF]) injection site reactions occurring within 7 days after each injection
- Occurrence of unsolicited (spontaneously reported) injection site reactions occurring within 28 days after each injection

Collection of systemic reactions and AEs:

- Occurrence of solicited (prelisted in the subject's DC and CRF) systemic reactions between the first and the second injections as well as between the second and the third injections, and up to 7 days after the remaining injections.
- Occurrence of unsolicited (spontaneously reported) systemic AEs between each injection and up to 28 days after the last injection.
- Occurrence of serious adverse events (SAEs) throughout the trial.

Other endpoints recorded or derived will be described at the time of statistical analysis plan. Depending on the item, these could include: nature (Medical Dictionary for Regulatory Activities [MedDRA] preferred term), time of onset, duration, number of days of occurrence, grade of severity, relationship to vaccine, action taken, whether the AE led to early termination from the study, seriousness, or outcome.

9.2.3 Safety Assessment Methods

9.2.3.1 Immediate Post-vaccination Surveillance Period

Subjects will be kept under observation for 30 minutes after each vaccination to ensure their safety. The post-vaccination surveillance should be documented in the source document. Any AE that occurs during this period will be noted on the source document and recorded in the CRF, as follows:

- Any unsolicited systemic AE occurring during the first 30 minutes post-vaccination will be recorded on the CRF as immediate unsolicited systemic AE.

- Solicited and unsolicited injection site reactions and solicited systemic reactions will not be actively solicited during the 30-minute period. If they occur within 30 minutes of vaccination, they will be recorded and analyzed as starting on the day of vaccination.
- Any SAE occurred during the first 30 minutes post-vaccination will be reported in the same way as any other SAE and to the Sponsor, according to the procedures described in [Section 10](#).

9.2.3.2 Reactogenicity (Solicited Reactions From Day 0 to Day 7 After Each Vaccination)

After each vaccination, subjects will be provided with a safety diary card, a digital thermometer, and a flexible ruler, and will be instructed how to use them. The following items will be recorded by the subjects in the diary card on the day of vaccination and for the next 7 days^a (i.e., D0 to D7) until resolution:

- Daily temperature, with the route by which it was taken
- Daily measurement or intensity grade of all other solicited injection site and systemic reactions
- Action taken for each event, if any (e.g., medication)

For solicited reactions still ongoing after the solicited period, daily intensity will be recorded in the DC until resolution of the reaction.

The action taken by the subject to treat any **solicited reactions** will be classified in the CRF using the following scale:

- 0: None
- 1: Medication (self-medication with an existing prescription or over-the-counter medication)
- 2: Health care provider contact (no new medication prescribed)
- 3: Health care provider contact and prescription of a new medication (health care provider instructed subject to take a new medication, either an over-the-counter medication or one requiring a written prescription)
- 4: Hospitalization (inpatient)

[Table 9.1](#) and [Table 9.2](#) present, respectively, the injection site reactions and systemic reactions that are prelisted in the diary cards and CRF, together with the intensity scales.

^a As applicable

Table 9.1: Solicited injection site reactions: terminology, definitions, and intensity scales

CRF term (MedDRA lowest level term [LLT])	Injection site pain	Injection site erythema	Injection site swelling
Diary card (DC) term	Pain	Redness	Swelling
Definition		Presence of a redness including the approximate point of needle entry	Swelling at or near the injection site Swelling or edema is caused by a fluid infiltration in tissue or cavity and, depending on the space available for the fluid to disperse, swelling may be either soft (typically) or firm (less typical) to touch and thus can be best described by looking at the size of the swelling
Intensity scale*	Grade 1: No interference with activity Grade 2: Some interference with activity Grade 3: Significant; prevents daily activity	Grade 1: ≥ 25 to ≤ 50 mm Grade 2: ≥ 51 to ≤ 100 mm Grade 3: > 100 mm	Grade 1: ≥ 25 to ≤ 50 mm Grade 2: ≥ 51 to ≤ 100 mm Grade 3: > 100 mm

* For the subjective reaction of pain, subjects will record the intensity level (Grade 1, 2, or 3) in the DC. For the measurable reactions of redness and swelling, they will record just the size of the reaction, and the classification as Grade 1, 2, or 3 will be assigned at the time of the statistical analysis

Table 9.2: Solicited Systemic Reactions: Terminology, Definitions, and Intensity Scales

CRF term (MedDRA lowest level term [LLT])	Fever	Headache	Malaise	Myalgia
Diary card term	Temperature	Headache	Feeling unwell	Muscle aches and pains
Definition	Elevation of temperature to $\geq 100.4^{\circ}\text{F}$	Pain or discomfort in the head or scalp. Does not include migraine.	General ill feeling. Malaise is a generalized feeling of discomfort, illness, or lack of well-being that can be associated with a disease state. It can be accompanied by a sensation of exhaustion or inadequate energy to accomplish usual activities.	Muscle aches and pains are common and can involve more than one muscle at the same time. Muscle pain can also involve the soft tissues that surround muscles. These structures, which are often referred to as connective tissues, include ligaments, tendons, and fascia (thick bands of tendons). Does not apply to muscle pain at the injection site which should be reported as injection site pain.
Intensity scale*	Grade 1: $\geq 38.0^{\circ}\text{C}$ to $\leq 38.4^{\circ}\text{C}$, or $\geq 100.4^{\circ}\text{F}$ to $\leq 101.1^{\circ}\text{F}$ Grade 2: $\geq 38.5^{\circ}\text{C}$ to $\leq 38.9^{\circ}\text{C}$, or $\geq 101.2^{\circ}\text{F}$ to $\leq 102.0^{\circ}\text{F}$ Grade 3: $\geq 39.0^{\circ}\text{C}$ or $\geq 102.1^{\circ}\text{F}$	Grade 1: No interference with activity Grade 2: Some interference with activity Grade 3: Significant; prevents daily activity	Grade 1: No interference with activity Grade 2: Some interference with activity Grade 3: Significant; prevents daily activity	Grade 1: No interference with activity Grade 2: Some interference with activity Grade 3: Significant; prevents daily activity

* For all reactions but fever, subjects will record the intensity level (Grade 1, 2, or 3) in the diary card. For fever, they will record the body temperature, and the classification as Grade 1, 2, or 3 will be assigned at the time of the statistical analysis.

Important notes for the accurate assessment of temperature:

Subjects are to measure body temperature once per day, preferably always at the same time. The optimal time for measurement is the evening, when body temperature is the highest. Temperature is also to be measured at the time of any apparent fever. The observed daily temperature and the route of measurement are to be recorded in the DC/MA, and the highest temperature will be recorded by the site in the CRF. The preferred route for this trial is oral. Pre-vaccination temperature is also systematically collected on the source document. Tympanic thermometers must not be used.

9.2.3.3 Unsolicited Non-serious Adverse Events From Day 0 to Day 28 After Each Vaccination

In addition to recording solicited reactions, subjects will be instructed to record any other medical events that may occur between each vaccination and during the 28-day period after the last vaccination. Space will be provided in the diary card for this purpose.

For each unsolicited non-serious AE, the following information is to be recorded:

- Start and stop dates^a
- Intensity of the event:
 - For measurable unsolicited non-serious AEs that are part of the list of solicited reactions, the size of the AE as well as the temperature for fever will be collected and analyzed based on the corresponding scale used for solicited reactions (see [Table 9.1](#) and [Table 9.2](#))
 - Other unsolicited non-serious AEs will be classified according to the following intensity scale:
 - Grade 1: No interference with activity
 - Grade 2: Some interference with activity
 - Grade 3: Significant; prevents daily activity
- Action taken for each AE, if any (e.g., medication)

The action taken by the subject to treat any **unsolicited AEs** will be classified in the CRF using the following scale:

0: None

1: Medication (self-medication with an existing prescription or over-the-counter medication)

2: Health care provider contact (no new medication prescribed)

^a The stop date of all related AEs will be actively solicited. For other events, the investigator will provide the stop date when it becomes available. AEs for which no stop date was obtained during the course of the trial will be considered as ongoing at the end of the trial.

3: Health care provider contact and prescription of a new medication (health care provider instructed subject to take a new medication, either an over-the-counter medication or one requiring a written prescription)

- Whether the AE led to study discontinuation
- Whether the AE was related to vaccination (for unsolicited systemic AEs)

The Investigator will assess the ***causal relationship*** between each unsolicited systemic AE and vaccination as either not related or related, based on the following definitions^a:

0: Not related – The AE is clearly / most probably caused by other etiologies such as subject's underlying condition, therapeutic intervention, or concomitant therapy; or the delay between vaccination and the onset of the AE is incompatible with a causal relationship; or the AE started before the first vaccination

1: Related – There is a “reasonable possibility” that the AE was caused by the vaccination, meaning that there is evidence or arguments to suggest a causal relationship

Note: By convention, all injection site AEs (solicited and unsolicited) and all solicited systemic reactions are considered to be related to vaccination and referred to as reactions, and therefore do not require the Investigator's opinion on relatedness.

AEs likely to be related to the product, whether serious or not, that persist at the end of the trial will be followed up by the Investigator until their complete disappearance or the stabilization of the subject's condition. The Investigator will inform the Sponsor of the date of final disappearance of the event.

